Any other form of non-IV intake received by the patients in the context of the therapy adopted (i.e. nutrition, solutions given for oral therapy).

OUTPUT

- *Urine output (ml)*
- *Blood loss (ml)*
- *Drainages (thorax, abdomen) (ml)*
- *Leak from other sites (estimation) (ml)*

Daily fluid balance

- *24 h fluid balance of the first 5 days (ml)*

Inclusion / Exclusion criteria

Inclusion Criteria:

- All consecutive adult (≥ 18 years old) patients admitted to ICU and expected to stay at least 48h.

Exclusion criteria:

- Planned admission after surgery for overnight ICU stay.
- Refusal of consent
- Moribund patients (i.e. expected survival < 24 h)

Endpoints

Primary aim: the primary aim is to describe the modality of fluid administration during the first 5 days of ICU stay considering 1) the overall fluid balance; 2) the characteristics of the fluids given; 3) the modality of fluid administration (i.e. FC and not FC).

Secondary aims:

- The secondary aim is to explore any association between fluid administration characteristics and clinical outcomes (see further)
- To evaluate factors potentially associated with the respective proportion of the different modalities of fluid administration
- To characterize FC administration modality in a large cohort of ICU patients.

Secondary clinical outcomes

- In-hospital mortality
- ICU mortality
- 30-days mortality
- Alive without any organ support (the number of calendar days between inclusion and 28 days that the patient is alive and with no requirement of cardiovascular, respiratory and renal support. Patients who die during ICU stay will have zero days counted for this variable, irrespective of vital support status)
- Organ dysfunction:
 - Lung
 - Time to cessation of mechanical ventilation during ICU stay [The number of calendar days between intubation / start of mechanical ventilation and extubation / liberation from mechanical ventilation, including non-invasive mechanical ventilation (maintained for at least 48 hours)].
 - Mechanical ventilation support-free days free days from day 1 to day 28. Cessation of mechanical ventilation support implies its complete interruption for at least 24 consecutive hours)

- Ventilation Associated Pneumonia (VAP) cumulative incidence (number of VAP per patient) and rate (number of VAP per 1000 days of MV) [22].
- Heart

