- Evolvement of central venous pressure (Time Frame: up to day 5 - highest and lowest value)
- Evolvement of central venous oxygen saturation (Time Frame: up to day 5 - worst value)
- Evolvement of central venous to arterial carbon dioxide difference (Time Frame: up to day 5 - worst value)

Statistical analysis

Data will be described as median and interquartile range (IQR) or number and percentage. Categorical variables were compared using Fisher's exact test and continuous variables using the nonparametric Wilcoxon test, Mann-Whitney test, or Kruskal-Wallis test.

In way to assess volume of fluid received, group-based trajectory modeling (GBTM) will be used to identify clusters of patients with similar patterns of fluid administration profile. GBTM is a semiparametric technique used to identify distinct subgroups of individuals following a similar pattern of changes over time for a given variable [23]. To do so, we will use the R-software “kml” package that implements the k-means algorithm in context of longitudinal data [24]. Briefly, longitudinal change in fluid received each day from day 1 to day 3 will be assessed. In way to avoid misinterpretation of findings due to time dependent competing events such death or ICU discharge, this analysis will be performed on patients alive and still in the ICU at day 3. The optimal number of clusters was evaluated using Calinski & Harabasz criterion [25].

In way to assess impact of fluid administration strategy, factors associated with in-hospital mortality, including identified cluster of fluid administration, will be assessed using mixed logistic regression where in-hospital mortality will be event of interest. Variables of interest will be selected according to their relevance and statistical significance in univariate analysis. We will use conditional stepwise regression with 0.2 as the critical P-value for entry into the model, and 0.1 as the P-value for removal. It will be planned a priori to force identified clusters and relevant variable related to hemodynamic instability in the model. Last, the center effect will be included as a random effect against the intercept. Should a center effect be identified, a secondary analysis in line with centers characteristics will be performed. Interactions and correlations between the explanatory variables will be checked. Continuous variables for which log-linearity will not confirmed, will be transformed into categorical variables according to median or IQR.

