For secondary outcomes, and in particular for day-30 mortality, number of days alive without vasopressors, mechanical ventilation or renal replacement therapy, will be assessed using survival analysis.

All tests will be two-sided, and P-value less than 0.05 will be considered statistically significant. Analyses will be performed using R software version 3.4.4 (<https://www.r-project.org>), including ‘kml’, ‘caret’, ‘lme4’, and ‘lmerTest’ packages.

Sample size

Considering the results of the FENICE study, we plan to enrol 10,000 patients and 15,000 FCs [30 patients / centre (max) and > 300 centres (min)]. The planned number of patients to be enrolled is in line with previous similar large observational trials regarding the use of fluids in ICU patients with the purpose of assessing current clinical practice and potential impact on clinical outcomes.

Data imputation

No data imputation will be performed on main outcome variables. Patients discharge alive from hospital, not admitted in rehabilitation unit or palliative care unit and/or lost of sight will be considered alive and free from organ support until day 30. Missing daily fluid volume will be imputed only if available every other day in which case it will be averaged.

Sensitivity analyses

In way to assess impact of fluid administration strategies, fluid volume considering only high chloride concentration fluids and impact of hypotonic fluids, three dedicated analyses using same methods than main analysis will be performed.

Ethical considerations and personal data protection

Patient protection

The responsible investigator will ensure that this study is conducted in agreement with either the Declaration of Helsinki or the laws and regulations of the country. The protocol has been written, and the study will be conducted according to Guideline for Good Clinical Practice. The protocol and its annexes are subject to review and approval by the competent Independent Ethics Committee(s) (“IEC”).

Subject identification

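### The tests stated for comparing fluid and fluid-challenge practice ignore clustering by centre and patient, so P-values will be too small for centre-level, centre-clustered and FC-level comparisons

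*Protocol*

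**What the plan says.** The Statistical analysis section of the Protocol describes data by medians with IQR, or counts with percentages. Categorical variables are to be compared with Fisher's "exact test and continuous variables using the nonparametric Wilcoxon test, Mann-Whitney test, or Kruskal-Wallis test". The same section sets a two-sided 0.05 significance threshold for all tests, so these comparisons are meant inferentially.

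Clustering is addressed once. In-hospital mortality "will be assessed using mixed logistic regression where in-hospital mortality will be event of interest", and in that model "the center effect will be included as a random effect against the intercept". No centre term is stated for any comparison of fluid or FC practice, and no patient-level term for repeated FCs appears anywhere.

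Two secondary aims under Endpoints concern practice variables. One is "To evaluate factors potentially associated with the respective proportion of the different modalities of fluid administration"; the other is to characterise how FCs are given. No method beyond the simple tests is stated for either. Under Sample size, "we plan to enrol 10,000 patients and 15,000 FCs", with at most 30 patients per centre and more than 300 centres.

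**The concern.** The Protocol itself presents fluid practice as a matter of local habit. The FC definition leaves the indication to the attending physician, following the unit's usual practice, and the Introduction says that neither FCs nor functional haemodynamic tests are standardised. Fluid type, FC volume, FC rate and use of functional tests are therefore likely to be more alike within a centre than between centres. The plan allows for a centre effect on mortality but states none for the practice variables, where one is at least as plausible.

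When the compared groups differ between centres (region and ICU type are the natural examples in a worldwide study), a test that counts every patient or FC as independent overstates the information. Differences between units could then be reported as significant well above the nominal 5%. At stake are the comparisons under the two secondary aims above, and possibly the screening step for the mortality model ("Variables of interest will be selected according to their relevance and statistical significance in univariate analysis") if it is run with the same simple tests.

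**Working it through.** **Inputs from the Protocol (Sample size; Statistical analysis).** 10,000 patients; 15,000 FCs; at most 30 patients per centre; more than 300 centres; two-sided alpha 0.05. No ICC, power or precision figure is given, so ICCs of 0.01 to 0.20 are assumed.

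**The plan's own figures.** 30 × 300 = 9,000, and 10,000 / 30 = 333.3, so at least 334 centres are needed, which agrees with more than 300. FCs per patient: 15,000 / 10,000 = 1.5. FCs per centre: 15,000 / 334 = 44.9, about 45.

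**Formulas.** Design effect DE = 1 + (m − 1) × ICC, with m the cluster size. Effective size = N / DE. Actual two-sided type I error of a nominal 5% test = 2 × [1 − Φ(1.96 / √DE)].

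**Centre-level factor.** Example at m = 30 and ICC 0.05: DE = 1 + 29 × 0.05 = 2.45; 1.96 / √2.45 = 1.25; type I error about 21%.

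| ICC (assumed) | DE, m = 30 | Effective N of 10,000 | Type I error, patients | DE, m = 45 | Type I error, FCs |
|---|---|---|---|---|---|
| 0.01 | 1.29 | 7,752 | 8% | 1.44 | 10% |
| 0.05 | 2.45 | 4,082 | 21% | 3.20 | 27% |
| 0.10 | 3.90 | 2,564 | 32% | 5.40 | 40% |
| 0.20 | 6.80 | 1,471 | 45% | 9.80 | 53% |

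**Check by simulation.** Mann-Whitney test, 334 centres of 30 patients, no true group difference, 1,000 runs per setting:

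- Factor fixed at centre level: 7%, 19%, 33% and 47% rejections at ICC 0.01, 0.05, 0.10 and 0.20, in line with the formula.
- Patient-level factor moderately clustered by centre (latent ICC of the factor 0.05 to 0.20): about 5% to 14%.
- Patient-level factor unrelated to centre: 4.7% to 5.6%, that is, nominal.
- Factor balanced within every centre (outcome ICC 0.05 to 0.20): 3.4% to 3.9%, slightly conservative.

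**FCs within patients alone.** Taking m = 1.5 for every patient, DE = 1 + 0.5 × 0.5 = 1.25 at ICC 0.5 (type I error 8%), and 1.5 at ICC 1 (11%). If FCs concentrate at 3 per recipient (assumed), DE at ICC 0.5 is 1 + 2 × 0.5 = 2.0 and the error is about 17%. Clustering by centre is the larger driver.

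**The case against.** The strongest reply is that the sentence on tests is generic. It is not tied to any named comparison, and no test by region or ICU type is specified. A statistical analysis plan may exist, and the software list includes lmerTest, which serves linear mixed models although only a logistic one is described, so further mixed models may be intended. This stands in part: the absence of a detailed model for the modality aim is not itself a fault. But the Protocol does state tests and a significance threshold. Applied as written to centre-level, centre-clustered or FC-level data, they give wrong P-values. A package name does not change the stated method.

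The inputs also lean high. Thirty is the maximum per centre. With 500 equal centres (assumed), m = 20 and ICC 0.05 gives DE = 1 + 19 × 0.05 = 1.95 and a type I error of about 16% rather than 21%. This stands, and the sizes must be read as conditional.

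A reader might infer that every comparison outside the mortality model is affected. The Protocol does not support that. Day-30 mortality and days alive without vasopressors, "mechanical ventilation or renal replacement therapy, will be assessed using survival analysis", which is not one of the tests at issue (though no centre term is stated there either). For sensitivity, "three dedicated analyses using same methods than main analysis will be performed", which can include the mixed model. Wilcoxon may also mean the signed-rank test, which allows for pairing within a patient.

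**Conclusion.** The point holds in a limited form. The tests stated for practice comparisons do not suit factors fixed at, or strongly clustered by, centre, nor FC-level comparisons across centres. For those, a nominal 5% test may run at about 8% to 45% (patients) or 10% to 53% (FCs). These ranges rest on assumed ICCs of 0.01 to 0.20, equal centres and, for patients, the maximum centre size. Repeated FCs within a patient add little on their own at an average of 1.5, more if FCs concentrate in fewer patients.

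Two wider conclusions are tempting and not supported. One is that P-values will be far too small throughout: for patient-level factors unrelated to centre they are about right, and for factors balanced within centres slightly too large. The other is that the primary result is invalid: the primary aim is descriptive, and its medians and percentages have no test attached. The harm falls on secondary comparisons, so this is a should-fix and not a must-fix.

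**What to change.** In the Statistical analysis section, state that inferential comparisons under the secondary aims on fluid modality and FC characterisation will use one of the following in place of the simple tests:

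- mixed models with a random intercept for centre, plus one for patient when the unit is the FC;
- GEE, allowing for the same clustering;
- a bootstrap that resamples whole centres.

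Report cluster-robust 95% confidence intervals for the key descriptors, and the ICC for the main practice variables. Keep Fisher, Mann-Whitney and Kruskal-Wallis, if at all, as descriptive only. It would be consistent to add a centre frailty or robust variance to the survival analyses.

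The cost is analysis wording: no added data or patients, and lme4 is already listed. The downside is wider intervals and fewer significant P-values.

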 - Time to cessation of vasopressor support during ICU stay (The number of hours between enrollment and complete stopping of vasopressor support (defined as its complete interruption for at least 24 consecutive hours).
 - Vasopressor support-free days during ICU stay from day 1 to day 28. Cessation of vasopressor support implies its complete interruption for at least 24 consecutive hours)
 - Inotropes-support free days
- Kidney
 - Time to cessation of Renal Replacement during ICU stay [The number of calendar days between start of renal replacement therapy and complete liberation from renal replacement therapy (at least 48 hours for continuous replacement modalities and 5 days for intermittent ones).
 - Renal Replacement support-free days during ICU stay from day 1 to day 28. Cessation of Renal Replacement support implies its complete interruption at least 48 hours for continuous replacement modalities and 5 days for intermittent ones)
 - Variation of creatinine-based KDIGO stage (Time Frame: 7 days after ICU admission). Renal function assessed according to KDIGO staging system from randomization through day 7 to assess for “de novo” or “worsening” acute kidney injury. Patients under chronic renal replacement therapy will not meet this end-point
- Variation in Sequential Organ Failure Assessment (SOFA) score (Time Frame: 7 days)

Sequential Organ Failure Assessment (SOFA) score calculated upon the maximum values observed on the day of enrollment and then, at days 2, 3, 4, 5 and 7 (or until patient discharge or death, if this happened before day-7), using clinically available data. If an individual organ dysfunction value is not available (i.e., cardiovascular, respiratory, renal, etc.), it will be assumed to be zero unless previous value was abnormal (in which case it would be considered the same organ score). Neurological score under sedation/invasive mechanical ventilation will be computed as that observed just before sedation/intubation.

Secondary functional outcomes

- Volume of resuscitation fluids (Time Frame: up to day 5). The volume of fluids administered with resuscitative intention up to 5 days from inclusion
 - Type of fluids
 - Modality of fluid administration
- Net fluid balance (Time Frame: up to day 5).
- Evolution of Capillary Refill Time (CRT) (Time Frame: up to day 5 - worst value)
- Evolution of Lactate levels (Time Frame: up to day 5 - worst value)

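### Organ-support outcomes start before the day 1-3 fluid cluster is complete, so recovery on days 1-3 can help decide which cluster a patient joins

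*Protocol*

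**What the plan says.** **Exposure.** Under Statistical analysis, the clusters come from a longitudinal k-means procedure in which "longitudinal change in fluid received each day from day 1 to day 3 will be assessed". Membership is therefore known only once day 3 is complete.

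**Population.** The same section says "this analysis will be performed on patients alive and still in the ICU at day 3". The reason given is to "avoid misinterpretation of findings due to time dependent competing events such death or ICU discharge". Stopping organ support is not mentioned.

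**Outcomes.** Under Endpoints, Secondary clinical outcomes:
- "Mechanical ventilation support-free days free days from day 1 to day 28"
- "Vasopressor support-free days during ICU stay from day 1 to day 28"
- "Renal Replacement support-free days during ICU stay from day 1 to day 28"
- Days alive without any organ support: "the number of calendar days between inclusion and 28 days that the patient is alive", with no support required.
- Time to vasopressor cessation: "The number of hours between enrollment and complete stopping of vasopressor support".
- Time to cessation of ventilation and of RRT: from the start of the support concerned.

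**Link between them.** The cluster is named as an explanatory variable in one model only, the mixed logistic model for in-hospital mortality. The secondary aim is to explore associations between the characteristics of fluid administration and clinical outcomes. The text then assigns survival analysis to 30-day mortality and to days alive without each support. It names neither an exposure nor a time origin at day 3.

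**The concern.** An exposure that takes three days to define should be related to outcomes that occur after those three days. Here the first three outcome days are the same days that define the exposure. A patient who comes off vasopressors on day 2 may be given less fluid on days 2 and 3 because of that recovery, and so be placed in a low-fluid cluster. The patient also collects more vasopressor-free days. The outcome has then shaped the exposure, and the comparison credits the low volume with a recovery that came first.

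The protocol recognises the problem for death and ICU discharge and handles it by restricting to patients present at day 3. That does nothing for patients who stop support on days 1-3 and remain in ICU. What is at stake is a secondary finding that lower fluid volumes shorten organ support, tested at two-sided 0.05 in a study of 10,000 patients, where even a modest artefact could reach significance.

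**Working it through.** **1. The clocks side by side.**

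| Item | Starts | Overlaps days 1-3? |
|---|---|---|
| Fluid cluster | day 1, complete at end of day 3 | – |
| Ventilator-, vasopressor-, RRT-free days | day 1 | yes |
| Days alive without organ support | inclusion | yes |
| Time to vasopressor cessation | enrolment | yes |
| Time to ventilation or RRT cessation | start of that support | only if it starts before the end of day 3 |
| In-hospital mortality | all analysed patients alive at day 3 | no |

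**2. The plan's own figures.** The protocol gives no power, effect size or event rate for these outcomes, so there is nothing to reproduce. Only the planned 10,000 patients is used below. Every other input is an assumption.

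**3. How many could stop early.** Assume everyone starts on support, with exponential time to cessation T and median 3 or 5 days. The share stopped by the end of day 3 is 1 − 2^(−3/3) = 0.50 or 1 − 2^(−3/5) = 0.34. With gamma frailty of variance 0.5 it is 1 − (1 + 0.5 × 3h)^(−2), where h = ln 2 / median. This gives 1 − 1.347^(−2) = 0.45 or 1 − 1.208^(−2) = 0.31. The range is 31-50%.

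**4. Null simulation with k-means.** There are 10,000 patients and 8 replicates per scenario, and fluid has no effect on T. Daily fluid = 2,000 ml + patient effect + daily noise (combined SD 1,000 ml) + extra × share of the day on support. Two clusters are formed from the three daily volumes. Support-free days = 28 − min(T, 28). Differences are low-fluid minus high-fluid. Ranges span both medians, with and without frailty.

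| Extra fluid on support | Difference, days 1-28 | Cessation rate ratio from day 1 | Clock moved to end of day 3, all patients | Clock moved, still on support only |
|---|---|---|---|---|
| 0 ml/day | −0.04 to 0.13 | 1.00-1.02 | −0.02 to 0.13 | −0.01 to 0.15 |
| 250 ml/day | 0.5 to 0.8 | 1.08-1.14 | 0.3 to 0.6 | −0.01 to 0.09 |
| 500 ml/day | 1.0 to 1.5 | 1.17-1.27 | 0.7 to 1.2 | −0.05 to 0.07 |
| 1,000 ml/day | 1.9 to 2.8 | 1.38-1.58 | 1.2 to 2.3 | −0.05 to 0.08 |

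Moving the clock without regard to support status leaves 64% (1.19/1.86) to 82% (2.31/2.82) of the false difference. Among patients still on support, the cessation rate ratio is 0.99-1.02 wherever fluid tracks support.

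**5. A second model, with ICU discharge.** Vasopressor duration is geometric with a Beta(2,6) daily hazard. Daily volume is N(2.0, 0.8) L plus the extra, and the three-day total is split at the median. For 0.25, 0.5 and 1.0 L/day extra:
- No discharge: 0.8, 1.7 and 3.1 false vasopressor-free days in favour of low fluid.
- 30% daily discharge once vasopressors stop, with patients gone by day 3 excluded as the protocol requires: 0.7, 1.3 and 2.4.
- 60% daily discharge, at 0.5 and 1.0 L/day: 0.7 and 1.3.

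Counting days 4-28 alone leaves about three quarters of the difference. Adding support status at day 3 as a covariate brings it to within 0.04 days of zero, and restricting to patients still on support to within 0.09.

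**6. What the near-zero results show.** In these models every patient still supported at the end of day 3 received the extra fluid on all three days, and support never restarts. The fix therefore removes the overlap almost by construction. It does not remove ordinary confounding by severity.

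**The case against.** - **The cluster is tied by name only to in-hospital mortality.** This stands. Its use for organ-support outcomes is implied by the secondary aim and by the survival-analysis sentence, not stated, and an SAP that is not at hand might set a day-3 origin. The point is therefore conditional. But the outcome clocks are fixed in the protocol, and any day 1-3 fluid measure meets the same overlap.
- **The day-3 restriction is already a landmark.** It is one for mortality. For organ support it is incomplete, because it conditions on being alive and in ICU and not on still being supported.
- **Not all cessation times start on day 1.** Correct. Only vasopressor cessation runs from enrolment. Ventilation and RRT run from the start of that support, which may fall before or after the end of day 3.
- **The size and direction are assumed.** Correct. With no extra fluid on support there is no bias. With 0.5 L/day less fluid on support the second model gives about 1.7 days the other way. The models also start every patient on support, while the protocol enrols all adults expected to stay at least 48 hours.

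A reader might also infer that the mortality analysis is biased, or wrong to leave out early deaths. The documents do not support that. Everyone analysed is alive at day 3, so no outcome precedes the exposure, and the restriction is stated openly with its reason. It limits whom the result describes. Nor does the protocol say that SOFA or KDIGO change will be compared by cluster.

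**Conclusion.** The point holds in conditional form. If the day 1-3 clusters are related to support-free days or to time to cessation as these are now defined, support that stops on days 1-3 can shape the exposure, and the present restriction does not prevent it. If fluid is higher while support runs, the low-fluid cluster gains a false advantage. This is illustratively about 0.5 to 3 support-free days for 0.25 to 1.0 L/day extra, and less when early recoverers leave ICU before day 3. The size in this cohort cannot be derived from the documents. It depends on how closely fluid follows support, how many patients stop support early and remain in ICU, and how many are on support at all. The mechanism needs only the first two to be non-zero. The in-hospital mortality model is not affected.

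**What to change.** For every comparison of organ-support outcomes between fluid clusters:

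1. Use the end of day 3 as time origin, and count support-free days over days 4-28.
2. Analyse time to cessation only in patients still on that support at the end of day 3.
3. Adjust the support-free-day comparisons for support status at the end of day 3. State how a patient whose interruption began during day 3 is classified, given the minimum interruption periods in the endpoint definitions.
4. If SOFA or KDIGO change is compared by cluster, take the change from day 3. SOFA is already scored on that day.
5. Word the cluster conclusions, including those on mortality, as applying to patients alive and in ICU at day 3.

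The day 1-28 outcomes can stay as they are for description of the cohort. The cost is a paragraph in the protocol or SAP and re-derivation from data the study already plans to collect. The price is an outcome window three days shorter and fewer patients at risk for time to cessation: in the first set of simulations, 31-50% had stopped by the end of day 3.

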Research question

What is the modality of fluid administration in ICU patients worldwide and what is the impact of fluid administration on clinical outcomes?

Aims

The primary aim of the FENICE II study is to describe the modality of fluid administration in the acute phase of resuscitation from hemodynamic instability in ICU patients.

As secondary aims, we'll appraise in-hospital, ICU and 30-day mortality and major organ dysfunction. Finally, we'll assess the use of variables (including clinical signs of hypovolemia, and indexes/images obtained from hemodynamic monitoring or echography) and functional hemodynamic tests to guide FC infusion in ICU patients, and the modality of FC administration (i.e. volume, rate, type of fluid), of evaluation of fluid responsiveness at the bedside.

Methods

Enrollment and study period

The phase of centers enrolment will be conducted over a time window of 12 months starting from 1st January 2024.

The phase of patients' enrolment will be conducted over a two-weeks period (14 days), chosen within a time window of 6 months starting from 1st January 2025.

The study period for data collection regarding the modality of fluid administration will consider the first 5 days from ICU admission (ICU days 1-5).

INPUT - Fluid data collection – definitions

Fluid Challenge/Fluid bolus (FC in test)

The FC is defined as the administration of any bolus of fluid (crystalloid or colloid) which is expected to affect pressure/flow/perfusion variables. The FC is expected to be completed within 30 min. Whenever possible, the exact time of fluid infusion will be collected. Considering the observational nature of the study, the indication for FC will be triggered by the decision of the attending ICU physician at the bedside (according to clinical practice of the ICU).

Continuous IV fluid administration (fluid maintenance or any other type of fluids given)

Any form of fluid infusion given for the purpose of optimizing overall fluid balance or to manage electrolytes (i.e. continuous infusion of any type of crystalloids). (*ml*)

Other IV fluids

Any form of fluid infusion received by the patients in the context of the therapy adopted (i.e. drugs solutions, glucose control, parenteral nutrition etc). (*ml*)

Blood products

Administration of red blood cells or fresh frozen plasma. (ml)

Other non IV intake

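### A single day 1-3 fluid cluster in one logistic model for hospital death can support an association, but not the impact of fluid strategy that the protocol reads from it

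*Protocol*

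**What the plan says.** The Statistical analysis section of the protocol fixes the exposure, the model and the reading.

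- **Exposure.** "longitudinal change in fluid received each day from day 1 to day 3 will be assessed", and trajectory modelling by k-means "will be used to identify clusters of patients with similar patterns of fluid administration profile". Each patient alive and in the ICU at day 3 gets one label.
- **Model.** Factors for death, with the cluster among them, "will be assessed using mixed logistic regression where in-hospital mortality will be event of interest".
- **Covariates.** "It will be planned a priori to force identified clusters and relevant variable related to hemodynamic instability in the model". Others enter by relevance, univariate significance and stepwise selection. The day on which covariates are measured is not stated.
- **Reading.** The purpose is given as "In way to assess impact of fluid administration strategy, factors associated with in-hospital mortality, including identified cluster of fluid administration". The Research question asks "what is the impact of fluid administration on clinical outcomes". The Summary, Sample size and Sensitivity analyses sections also use the word *impact*.
- **Reading elsewhere.** Under Endpoints, the secondary aim is only to "explore any association between fluid administration characteristics and clinical outcomes".
- **How fluid is given.** Under the fluid challenge definition, "the indication for FC will be triggered by the decision of the attending ICU physician at the bedside".

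**The concern.** Fluid on days 2 and 3 is given to a patient whose course since admission is already visible to the physician. A patient who fails to improve may receive more fluid and is also more likely to die. A label built from all three days mixes this response to illness with any effect of fluid, and one regression with one fixed covariate set cannot separate them.

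Nothing else in the plan does so either. The day-3 restriction is justified only by competing death and discharge. The centre intercept deals with differences between units. The three sensitivity analyses use the same methods, so they would share the bias and could look like confirmation. SOFA on days 2 and 3 and daily lactate are collected but given no stated role in this model.

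With 10,000 patients planned, a biased odds ratio would look precise. At stake is whether the study reports that a fluid strategy raises mortality when it has only described which patients receive more fluid.

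**Working it through.** The protocol gives no mortality rate, effect size or power, so there is no stated figure to reproduce. The check is by simulation. **All inputs below are assumptions**, and centre effects and stepwise selection are left out.

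**Step 1. No effect of fluid, severity as a random walk.**
- Severity: S1 ~ N(0,1), S2 = S1 + d·e, S3 = S2 + d·e, with e ~ N(0,1).
- Daily volume in litres: F = 3 + g·S (same day) + noise, SD 1.
- Death: logit P = -1.7 + 0.8·S3, with no fluid term, so the true odds ratio is 1.00. Mortality is 18-20%.
- k-means with k from 2 to 4 chosen by Calinski-Harabasz, then logistic regression of death on cluster. n = 5,000, 100 runs.

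Highest versus lowest cluster, odds ratio (share of runs with P<0.05):

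| g | d | Day-1 severity only | Day 1-3 severity, exact |
|---|---|---|---|
| 0 | 0.7 | 1.00 (7%) | 1.00 (7%) |
| 0.1 | 0.7 | 1.10 (15%) | 0.99 (8%) |
| 0.3 | 0.7 | 1.37 (100%) | 0.99 (6%) |
| 0.5 | 0.7 | 1.67 (100%) | 0.99 (5%) |
| 0.5 | 0.3 | 1.11 (24%) | 1.00 (7%) |
| 1.0 | 0.7 | 2.27 (100%) | 0.99 (9%) |

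The day-1 correlation of volume with severity is g/√(1+g²): 0.10, 0.29, 0.45 and 0.71 for g = 0.1, 0.3, 0.5 and 1.0. The last row is therefore extreme. If severity is measured with error (SD 0.5) at g = 0.5 and d = 0.7, adjustment for days 1-3 leaves 1.09 (17%). At n = 10,000 the day-1-only bias is the same size, but at g = 0.1 it is significant in 28% of runs instead of 15%.

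**Step 2. No effect of fluid, a different severity model.** Severity is AR(1) with coefficient 0.5, 0.7 or 0.85. Mean volumes are 3, 2.5 and 2 litres, SD 1. Logit P(death) = -1.5 + 0.8·S3, giving 21% mortality. Adjustment for admission severity is perfect.

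| Correlation of volume with same-day severity | Cluster odds ratio |
|---|---|
| 0.2 | 1.06-1.09 |
| 0.3 | 1.17-1.26 |
| 0.4 | 1.28-1.45 |
| 0.5 | 1.33-1.58 |

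Repeat codings gave upper ends of 1.62 and 1.65, and one gave 1.14-1.19 at correlation 0.2 when four clusters were chosen, so the second decimal depends on the cluster solution. Halving the slope of death on severity (coefficient 0.7) gives 1.08-1.25 across correlations 0.2-0.5. With 6,000 patients assumed, correlation 0.3 and coefficient 0.7, P<0.05 occurred in 79% of 200 runs in one coding and 87% of 60 in another.

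**Step 3. Fluid has a real effect.** Next-day severity = S + a·(F - 3) + 0.7·e, with g = 0.5 and two clusters. Logit P(death) = -1.9 + 0.8 × severity after day 3.

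| a | True odds ratio | Day-1 covariates | Day 1-3 covariates |
|---|---|---|---|
| 0 | 1.00 | 1.69 | 1.04 |
| -0.15 | 0.71 | 1.25 | 0.89 |
| +0.15 | 1.50 | 2.35 | 1.18 |

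The 1.04 is simulation error; fresh runs sit at about 1.00. The true values are marginal and the model values conditional, so small differences mean little. The pattern is clear all the same: day-1 covariates turn a benefit into apparent harm, and day 1-3 covariates pull both real effects towards 1.

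**Step 4. Day-1 volume as exposure.** In the Step 2 setting, day-1 volume adjusted for exact admission severity gives 0.99-1.02 per litre. With severity measured with error (SD 0.5) it rises to as much as 1.07.

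**The case against.** A reader might infer that the planned model must produce excess mortality in the high-volume cluster even if fluid does nothing. The protocol does not support that. It does not confine covariates to admission, it forces in a variable for haemodynamic instability, and it collects SOFA and lactate daily. Covariate timing may properly be left to the SAP. Under a null effect, well-measured severity through day 3 brings the odds ratio back to about 1.00 (Step 1). This objection stands, and the bias is likely only with admission covariates.

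The size is also open to challenge. None of the inputs is in the protocol. The statement about bedside decisions covers fluid challenges only, while the trajectory uses all fluid received. The Introduction cites a cohort in which resuscitation fluid was 6.5% of mean daily volume, against 24.7% for maintenance and replacement and 32.6% for fluid creep. The Sample size section plans 15,000/10,000 = 1.5 challenges per patient. Other fluids may track severity too, but the protocol does not show how strongly. This also stands: the figures are illustrative.

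Finally, the primary aim is descriptive, and the sentence that announces the model itself speaks of associated factors. That makes the point cheaper to fix but does not remove it, because the same sentence gives impact as its purpose. Nor does later adjustment rescue that reading, as Step 3 shows.

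**Conclusion.** The point holds as a mismatch between what the model can show and what the protocol says it shows. The protocol itself fixes a three-day exposure, one label, one regression and an impact reading, so this is not detail awaiting an SAP.

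With admission covariates only, a null effect is likely to appear as an odds ratio of about 1.06 to 1.6 where volume correlates 0.2 to 0.5 with same-day severity. It is smaller with slow change in severity or a weak fluid response, and larger only under more extreme inputs. With day 1-3 covariates the null bias largely goes, but real effects are attenuated. The direction and the absence of a workable single covariate day rest on the structure of the model; the sizes rest wholly on assumption. That the bias is certain, or that any particular share of null trials would reach significance, is not established.

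**What to change.** 1. Replace *impact* with *association* in the Summary, Research question, Statistical analysis, Sample size and Sensitivity analyses sections, in line with the secondary aim under Endpoints. State that the trajectory odds ratio is descriptive and is not an effect of fluid strategy.
2. Beside the cluster result, report the same mixed model with day-1 fluid volume as exposure, adjusted only for severity recorded at admission before that fluid. The planned SOFA uses the maximum values on the enrolment day. If nothing earlier is available, state that it is concurrent with day-1 fluid and that residual confounding remains.

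A marginal structural model weighted on severity known at the start of each day is not proposed. In the Step 2 setting (correlations 0.3-0.5), weighting on previous-day severity left 1.05-1.17 per litre, against 1.06-1.18 for cumulative volume adjusted for admission severity.

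The cost is wording in five sections, one extra model and a more modest mortality claim. The extra model needs no new data unless pre-fluid severity has to be added to the case report form.
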